5.7.3.2. Analysis of Symptoms of Infection with Coronavirus-19 (SIC)

The number and percentage of participants with at least one SARS-CoV-2 infection will be tabulated by vaccination schedule.

In the group of participants seronegative at baseline, the number and percentage of participants with at least one positive N-ELISA, if available, will be tabulated.

For each participant with COVID-19 infection, a narrative will be prepared based on the visit performed 28 days after the onset of COVID-19 signs and symptoms and other selected information from the clinical database, as available:

- participant ID
- vaccination regimen
- sex, race, ethnicity, age, BMI, dates at which vaccinations were received
- pulse oximetry
- physical examination findings based on the visit performed 28 days after the onset of COVID-19 signs and symptoms
- vital signs including body temperature based on the visit performed 28 days after the onset of COVID-19 signs and symptoms
- Humoral immune responses as collected at the planned time points + those obtained from the blood sample taken on the visits performed 3 and 28 days after the onset of COVID-19 signs and symptoms. This information may be presented graphically.

For the analysis of the SIC (Patient Reported Outcomes, PRO) data, the following considerations apply:

- A COVID-19 infection "episode" is defined as a period starting from the first day on which any symptoms is reported until the last day any symptom is reported, within an interval stating up to 5 days prior to a positive PCR test and finishing up and to 42 days after it
- A symptom (e.g. feeling generally unwell, fatigue, physical weakness, cough, etc.) is assumed to be present on each day the associated Yes/No question is answered "Yes" or the associated severity question has a rating > 0.
- If the PRO was not completed due to the participant being too ill or due to the participant being hospitalized, the symptom will be considered present with maximum severity score. If the PRO was completed due to any other reason, no imputations will be done.

Duration of the episode will be calculated as (the end date of the last symptom in that episode – the start date of the first symptom in that episode) + 1. Duration of each symptom will be calculated as last date of symptom reporting – its first date + 1.

The following analyses will be conducted for confirmed SARS-CoV-2 infection cases:

- For the first infection episodes, the following statistics will be calculated: number of subject with an episode, the mean and median duration of episodes (with min, max, q1 and q3), and mean and median number of symptoms reported per episode (with min, max, q1 and q3).
- At the level of the symptoms for an infection episode, the following statistics will be calculated: number of participants experiencing the symptom, mean and median duration of each symptom (with min, max, q1 and q3), median (with min, max, q1 and q3) of highest

severity of each symptom, median duration of the highest severity of each symptom (with min, max, q1 and q3).

In addition, participant listings will be provided containing the SIC information for each time point. Details about these analyses will be provided in the DPS.

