5.7.3. COVID-19 signs and symptoms

5.7.3.1. Symptoms of Infection with Coronavirus-19 (SIC)

The SIC is a disease-specific patient-reported outcome (PRO) instrument that is completed by the participant. The SIC has a total of 30 items assessing signs and symptoms of COVID-19. The first 25 items, the participant indicates "yes" or "no" if they have a symptom and if "yes" report a severity from 0 (none) to 10 (worst possible). The second part has the participant enter their temperature, and the third part has the participant record "yes" or "no" (absence or presence of additional signs and symptoms), where severity cannot be assessed). The analyses are conducted in two ways, by part 1, part 2 and part 3, scored separately, and also grouped into related categories for composite scoring.

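### The SIC imputation rule scores any hospital-missed diary at maximum severity, so in a confirmed SARS-CoV-2 case a delivery admission inside the episode interval can be counted as worst-possible COVID-19

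*SAP*

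**What the plan says.** SAP Section 5.7.3.1 describes the instrument: "The SIC has a total of 30 items assessing signs and symptoms of COVID-19". The first 25 items carry a severity rating from 0 to 10; the rest are temperature and yes/no items.

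Section 5.7.3.2 places an episode "within an interval stating up to 5 days prior to a positive PCR test and finishing up and to 42 days after it". On missing diaries it begins "If the PRO was not completed due to the participant being too ill or due to the participant being hospitalized"; the second trigger and its consequence read together as "due to the participant being hospitalized, the symptom will be considered present with maximum severity score". The next sentence reads "If the PRO was completed due to any other reason, no imputations will be done"; the sense requires *not completed*.

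The summaries are introduced by "The following analyses will be conducted for confirmed SARS-CoV-2 infection cases". They cover episode duration, number of symptoms per episode, number of participants experiencing each symptom, symptom duration, highest severity of each symptom, and duration of that highest severity.

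Section 5.7.2 adds two relevant rules. COVID-19 episodes are not adjudicated, and a sign or symptom not observed in the eCOA or eCRF counts as absent.

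**The concern.** Scoring a hospital-missed diary at the ceiling is defensible where admission is itself a sign of severe disease. Here the two triggers, too ill and hospitalized, are joined by *or*, and neither is tied to COVID-19. Section 1.2 enrols women at gestational weeks 16 to 38 and the study continues to about 12 months after delivery, so delivery is expected during follow-up, and an admission for it (or for another obstetric reason) satisfies the rule.

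Highest severity is a maximum over the episode. One imputed day therefore displaces everything the participant actually recorded, and the duration of highest severity becomes the duration of the imputed days. At stake is the description of COVID-19 severity in vaccinated pregnant women, a named exploratory objective. Confirmed cases may be few, in which case each distorted case weighs noticeably.

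**Working it through.** The plan gives no figure on this point, so there is none to reproduce. Two things can be checked: what one imputed day does, and how often a delivery can fall in the interval.

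**1. Effect of one imputed day (assumed data).** Take a mild case: 3 of the 25 rated symptoms, each at severity 2, on days 1 to 5.

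- As observed: 3 symptoms, summed highest severity 3 × 2 = 6 out of 25 × 10 = 250, duration 5 − 1 + 1 = 5 days.
- One diary wholly missed in hospital between days 1 and 5: all 25 items become present at 10, so the sum is 250. The missed day lies within the reported span, so highest severity is overridden on any reading.
- One diary missed on day 30: if imputed days count as reported, 25 symptoms at 10 and a duration of 30 − 1 + 1 = 30 days. If they do not, day 30 lies outside the episode and nothing changes.

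The SAP does not choose between the last two outcomes. It defines the episode, the symptom count and symptom duration by days or symptoms *reported*, but episode duration by the end date of the last symptom, and it calls an imputed symptom *present*. Reading *the symptom* as all 25 items is the natural reading for a wholly missed diary. Yes/no items can only be set to present, and temperature is not addressed.

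**2. Reach.** A diary missed on delivery day D falls in the interval if the PCR date lies from D − 42 to D + 5, which is 48 days, cut off at vaccination. Assumptions: delivery at week 40, follow-up to 366 days postpartum, PCR dates uniform over follow-up, a single missed day. With d = (40 − entry week) × 7, the share is (min(42, d) + 6)/(d + 366).

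| Entry week | d | Share of confirmed cases |
|---|---|---|
| 16 | 168 | 48/534 = 9.0% |
| 22 | 126 | 48/492 = 9.8% |
| 28 | 84 | 48/450 = 10.7% |
| 34 | 42 | 48/408 = 11.8% |
| 38 | 14 | 20/380 = 5.3% |

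This is the share with delivery inside the interval. The affected share is this multiplied by the probability that a diary was due and recorded as missed for hospitalization, which the SAP does not give. Testing at admission would raise the share.

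**3. Which summaries move.** Suppose 10 confirmed cases, one of them imputed, with the other nine like the mild case.

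- If imputed days count as reported, mean duration is (9 × 5 + 30)/10 = 7.5 days against 5, and mean symptom count is (9 × 3 + 25)/10 = 5.2 against 3. The medians stay at 5 and 3.
- Suppose highest severity is summarized among women with the symptom. If 3 women report it at severity 2, the values become 2, 2, 2, 10: median 2, maximum 10. If 1 woman reports it, they become 2, 10: median 6. If nobody reports it, the symptom now appears in 1 of 10 women with median 10.

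Medians for common symptoms are fairly safe. Per-symptom counts, means, maxima and, as more cases are affected, upper quartiles are more exposed, and for rare symptoms so is the median.

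**The case against.** The best defence is that several conditions must coincide. A reader might infer that any participant admitted to give birth is scored as having worst-possible COVID-19. The SAP does not say that: without confirmed infection she does not enter these tables, and the admission must also fall in the interval with a due diary recorded as missed for hospitalization. This stands, and the point is confined accordingly.

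A reader might also infer that a 5-day episode can stretch to 48 days, the full interval, or that an asymptomatic PCR-positive woman becomes a maximal case. Both require imputed days to count as reported and a diary still to be due at the time. The SAP leaves the first unclear; the diary schedule belongs to the protocol, which is not at hand. If collection stops when symptoms resolve, a recovered woman who delivers weeks later has no diary to miss.

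Nor is half of cases a fair size. With 84 days from vaccination to delivery, 42/84 = 50% of antenatal infections precede delivery by no more than 42 days, but the summaries cover infections throughout follow-up.

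Finally, the endpoint is exploratory, no hypothesis is tested, and the planned narratives and SIC listings would let someone notice an isolated day of maximum scores. That limits the consequence but does not correct the tables. Further detail is deferred to the DPS, but the rule in the SAP is already explicit and unqualified.

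**Conclusion.** The rule is wrong for this population as written. It treats hospitalization for any reason as maximal COVID-19, and nothing else in the SAP prevents that; Section 5.7.2 rules out adjudication, and its own presence rule points the opposite way. The effect is limited to confirmed cases meeting the conditions above. Delivery falls in the interval for about 5% to 12% of confirmed cases by entry week, under uniform infection dates and delivery at week 40; the affected share is smaller by an unknown amount. Within an affected episode the override of highest severity is complete for the rated items. Inflation of symptom counts and durations is possible, not established. No primary or secondary conclusion depends on this. It should be changed because the error is systematic, runs towards greater severity, and is easy to remove.

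**What to change.** In Section 5.7.3.2:

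- Restrict the maximum-severity imputation to diaries missed because the participant was too ill from COVID-19 or hospitalized for COVID-19, using the recorded reason for admission.
- Leave diaries missed during admission for delivery or any other reason as missing.
- State that imputed days do not extend episode or symptom duration.
- Correct the following sentence to say *not completed* due to any other reason.
- Reconcile the rule with Section 5.7.2, which treats unobserved symptoms as absent, for example by naming the COVID-19 imputation there as the sole exception.

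The cost is SAP wording, one added condition in the derivation, and slightly fewer imputed diary days.

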5.7.4. Demographics and Baseline Characteristics

Demographic and baseline variables will be summarized by vaccination schedule and overall for the FAS. In addition, the distribution of participants by country and site ID will be presented unless otherwise noted.

SARS-CoV-2 Serostatus at baseline will be derived from S- and/or N-serology at baseline, and the definition will depend on the participant's previous vaccination history.

Details are provided in Section 6.3.

5.7.5. Definition of Subgroups

For key safety and immunogenicity analyses (S-ELISA, MSD 4-plex and VNA), results will be analyzed by gestational age group at screening and by SARS-CoV-2 serostatus at baseline. Results will be presented by previous vaccination group like other reports.

Subgroups are defined as shown in Table 6 while the derivation of the SARS-CoV-2 Serostatus at baseline is described in Table 7.

Subgroup analysis will ignore unknown, missing and not reported values, unless otherwise specified.

Subgroup	Definition
(at baseline/screening)	
Age Group	• 18-34 years (≥18y to <35y)
	• 35-45 years (≥35y to ≤45y)
Gestational Age Group	• 16-27 weeks (≥16w to <28w)
	• 28-38 weeks (≥28y to ≤38w)
BMI	• underweight $<18.5 \text{ kg/m}^2$
	• normal $18.5 - <25 \text{ kg/m}^2$
	• overweight and obese $>=25 \text{ kg/m}^2$
Race	• Asian
	Black or African American
	• White
	• Other ('Multiple ^a or 'Native Hawaiian or other Pacific Islander' or
	'American Indian or Alaska Native')
Ethnicity	Hispanic or Latino
	Not Hispanic or Latino
SARS-CoV-2 Serostatus	• Negative
	 Not Negative (excluding missing)

Table 6:	Definition	of Subgroups
		0 1

^a If multiple race categories are indicated, the Race is recorded as 'Multiple'.

Vaccination history	SARS-CoV-2 Serostatus at baseline (by N and/or S serology for vaccine naïve, and by N-serology for previously vaccinated individuals) to assess previous infections	Serostatus result at Baseline
Vaccine naïve (Group 4)	If positive in either Roche Elecsys (N serology) or S-Elisa, or both	Positive
	If negative in both	Negative
	If both are missing	Missing
Other vaccines (and no inactive vaccine) based on S protein	If positive by Roche Elecsys (N serology) only (regardless of the S-ELISA result)	Positive
(Moderna, Pfizer, AstraZeneca, Janssen, Sputnik, Novavax)	If negative by Roche Elecsys (N serology) only (regardless of the S-ELISA result)	Negative
	If Roche Elecsys (N serology) is missing (S- ELISA is not used here)	Missing
Others; depends on vaccine		
Inactivated vaccines (e.g. Sinovac, Sinopharm) or combination of vaccines including at least one inactivated vaccine	Since participant is previously vaccinated with an inactivated vaccine, it is not possible to determine serostatus at baseline	Not evaluable

 Table 7:
 Definition of SARS CoV 2 Serostatus at Baseline

For infants, immunogenicity analyses will be conducted based on the subgroup of the mother at baseline/screening (gestational age group, age, BMI, race, SARS-CoV-2 serostatus).

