1.2. Study Design

This is an open-label multicenter, Phase 2 study in healthy pregnant (2nd and/or 3rd trimester of pregnancy) participants ≥ 18 to ≤ 45 years of age to evaluate safety, reactogenicity, immunogenicity, and pregnancy outcomes. In this study, Ad26.COV2.S will be assessed as a single dose of 5×10^{10} vp in pregnant women who were previously vaccinated with another COVID-19 vaccine regimen or who were vaccine naïve at study entry.

A target of 240 adult participants in the 2nd or 3rd trimester of pregnancy (Week 16 to Week 38 of gestation, inclusive) was to be enrolled. Efforts were made to ensure good representation in terms of race and ethnicity. Enrollment was staggered and started with recruitment of vaccine naïve Sentinel participants (n=5) followed by an additional larger Safety Cohort (n=17) who all received 1 dose of Ad26.COV2.S vaccine at 5×10^{10} vp. Based on the safety data of those subjects, the IDMC confirmed that the safety profile of 1 dose of Ad26.COV2.S at 5×10^{10} vp was considered acceptable and no safety concerns were identified. The remaining participants (who have received their last COVID-19 vaccination at least 4 months prior to receiving the study vaccine or are vaccine naïve participants) were to be enrolled to receive 1 dose of Ad26.COV2.S at 5×10^{10} vp. They will preferably be equally distributed between the following groups, per their COVID-19 vaccination histories:

- **Group 1**: Previous primary vaccination (2-doses) or homologous booster vaccination with Comirnaty (Pfizer-BioNTech) or SpikeVax (Moderna)
- **Group 2**: Previous primary vaccination (1-dose) or homologous booster vaccination with Ad26.COV2.S (Janssen)
- **Group 3**: Previous COVID-19 vaccination, irrespective of previous schedule and vaccine (includes heterologous regimens) and excluding schedules for Groups 1 and 2
- Group 4: Vaccine naïve participants, including those who are in Sentinel and Safety Cohorts

Prior to CTP amendment 4, the sample size of each of the groups was preferably equally distributed but flexible with a target to recruit at least 40 participants in Groups 1 to 3 and at least 25 participants in Group 4. Participants were stratified by pregnancy stage at the time of enrollment (Weeks ≥ 16 to < 28 or Weeks ≥ 28 to ≤ 38), with a goal of at least approximately 25% participants per trimester, per group.

As of CTP amendment 7, participant enrolment in this study was ceased.

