6.3. Appendix 3 Demographics and Baseline Characteristics

Table 8 presents a list of the demographic variables that will be summarized by vaccination group and overall for the FAS-A analysis set. Demographics will also be summarized by country using the FAS-A analysis set.

Continuous Variables:	Summary Type
Age ([years])	
Weight (kg)	descriptive statistics (N, mean,
Height (cm)	and range [minimum and
Body Mass Index (BMI) (kg/m2) : (underweight <18.5 kg/m2; normal 18.5 - <25 kg/m2; overweight 25 - <30 kg/m2; and obese >=30 kg/m2)	maximum]
Categorical Variables:	
Age Group (18-34 years, 35-45 years)	
Gestational Age (16-27 weeks, 28-38 weeks)	
SARS-CoV-2 Serostatus at Baseline (Positive, Negative, Not evaluable,	
Missing)	
Race ^a (American Indian or Alaska Native, Asian, Black or African	
American, Native Hawaiian or other Pacific Islander, White, Not reported,	
Unknown)	Frequency distribution with the
Country (Country 1, Country 2,)	number and percentage of
Ethnicity (Hispanic or Latino, Not Hispanic or Latino, Not reported,	participants in each category.
Unknown)	
SARS-CoV-2 RNA Nasal Swab at Baseline (Positive, Negative, Missing)	
RT-PCR (Positive, Negative)	
Participant Educational Level	
Participant Living Status]
Participant Profession	

Table 8: Demographic Variables

^a If multiple race categories are indicated, the Race is recorded as 'Multiple'

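### As Table 6 is worded, the Not Negative serostatus subgroup pools seropositive women with inactivated-vaccine recipients whose serostatus the SAP says cannot be determined (Group 3, the overall column and their infants only)

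*SAP*

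**What the plan says.** Section 5.7.5 defines the serostatus subgroup in Table 6 with two levels, Negative and "Not Negative (excluding missing"). The underlying variable is derived in Table 7, whose column header gives its purpose: N and/or S serology for vaccine-naïve women, and "by N-serology for previously vaccinated individuals) to assess previous infections". Table 7 assigns Positive, Negative, Missing or Not evaluable. Not evaluable covers inactivated vaccines and any "combination of vaccines including at least one inactivated vaccine", with the reason: "Since participant is previously vaccinated with an inactivated vaccine, it is not possible to determine serostatus at baseline".

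The same section has a general exclusion rule: "Subgroup analysis will ignore unknown, missing and not reported values, unless otherwise specified". Appendix 3 (Section 6.3, Table 8) tabulates "SARS-CoV-2 Serostatus at Baseline (Positive, Negative, Not evaluable" and, as a further category, Missing.

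Serostatus is a named subgroup factor for the primary endpoints (Section 5.3.3), for key secondary safety analyses (Section 5.4.3), and for key safety and S-ELISA, MSD and VNA results (Section 5.7.5). Section 5.7.5 also carries the mother's subgroup, including serostatus, over to the infant immunogenicity analyses.

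**The concern.** A woman whose serostatus the SAP declares undeterminable is placed in the level that otherwise means seropositive. The sorting is one-sided by construction: under Table 7 an inactivated-vaccine recipient can never be Negative, so all such women sit on one side of the contrast and none on the other. Where they were enrolled, a comparison derived to reflect previous infection also compares previous vaccine platforms.

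The study is descriptive, so no error rate or sample size is at stake. What is at stake is how a reader interprets the subgroup tables for safety and antibody response, and the matching infant tables. The SAP gives no reason for the pooling and plans no analysis without it.

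**Working it through.** **Step 1: which results fall in Not Negative.** Table 7 results: {Positive, Negative, Missing, Not evaluable}. Table 6 removes Negative and Missing. What remains is {Positive, Not evaluable}.

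**Step 2: whether another rule removes Not evaluable.** The general rule lists unknown, missing and not reported values. Not evaluable is not named. Table 8 keeps it apart from Missing. Table 6 says Not Negative rather than Positive, although after excluding missing values the two would coincide if Not evaluable were also meant to drop out. Read literally, the pooling stands.

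**Step 3: where it can occur.** Under Section 1.2, Group 1 has Pfizer-BioNTech or Moderna histories, Group 2 Janssen, and Group 4 is vaccine naïve. None can receive the Not evaluable result. Group 3 takes any other history, "irrespective of previous schedule and vaccine (includes heterologous regimens) and excluding schedules for Groups 1 and 2", so it can. Section 5.7.5 presents subgroup results by previous vaccination group, and Section 5.1 adds an overall summary. The affected displays are therefore Group 3, the overall column, and the infants of those mothers.

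**Step 4: size, by assumption.** The SAP has no figure to reproduce: it states neither the number of inactivated-vaccine recipients nor the seropositivity rate. Let *n* be the group size, *k* the number of inactivated-vaccine recipients and *p* the positivity among the others, ignoring missing results. Then

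share of Not Negative that is Not evaluable = *k* / (*k* + (*n* − *k*)·*p*).

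Take *n* = 60 for Group 3 (the target of 240 split equally over four groups) and *p* from 0.3 to 0.7 (assumed):

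| *k* | *p* = 0.7 | *p* = 0.3 |
|---|---|---|
| 0 | 0% | 0% |
| 2 | 2/42.6 = 4.7% | 2/19.4 = 10.3% |
| 5 | 5/43.5 = 11.49% | 5/21.5 = 23.3% |
| 20 | 20/48 = 41.7% | 20/32 = 62.5% |

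At the stated minimum of *n* = 40, 5 such women give 5/29.5 = 16.9% to 5/15.5 = 32.3%. In the overall column, with *n* = 240 and the same *p* throughout, 5 women give 5/169.5 = 2.9% to 5/75.5 = 6.6%, and 20 women give 20/174 = 11.49% to 20/86 = 23.3%. Enrolment ceased at protocol amendment 7, so actual group sizes may differ from all of these.

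**Step 5: after the change.** With levels Negative and Positive, the share is 0% for every *k*.

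**The case against.** The best defence is that the SAP already excludes these women: a serostatus that cannot be determined is, in ordinary language, unknown, and the general rule ignores unknown values. This is a possible reading, but the text does not state it, and Tables 6 and 8 point the other way. A programmer following Table 6 would pool. If exclusion was intended, the wording still needs correcting.

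A second defence is that Negative versus Not Negative is deliberate: it keeps the reference level clean and labels the other level honestly as not shown to be negative. It is true that the label does not claim infection. But the variable is derived to assess previous infections, and the SAP does not explain why women it cannot classify should join the seropositive ones.

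Third, the consequence is limited and partly visible. No hypothesis is tested, the main summaries by group and overall are unchanged, and Table 8 shows how many women are Not evaluable. All of this stands and bounds the importance of the point.

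A reader might also infer more than the documents support:

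- That the subgroup fails to reflect previous infection throughout the trial. It does not fail in Groups 1, 2 and 4.
- That the Positive women have proven infection. Table 7 says only seropositive, and for vaccine-naïve women a positive S-ELISA alone is enough.
- That any effect of previous infection is diluted. The direction depends on how inactivated-vaccine recipients compare with seropositive women, which the SAP does not report.
- That most of the subgroup is unclassifiable. That needs a large assumed count; with zero or few such women the effect is nil or small.

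**Conclusion.** Wrong as written. That Not Negative equals Positive plus Not evaluable follows from Tables 6 and 7 and needs no outside figure. The consequence is confined to Group 3, the overall column and the infants of the affected mothers. There the contrast is confounded with previous vaccine platform if inactivated-vaccine recipients were enrolled. Neither direction nor size can be established from the SAP: the shares in the working are illustrations that rest on assumed group size, count and positivity, and they start at zero. Since the analysis is descriptive, this should be corrected for the sake of interpretation; it does not threaten the trial's main results.

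**What to change.** In Table 6, define the serostatus subgroup as Negative versus Positive, as derived in Table 7. State explicitly that Not evaluable is excluded from that contrast, and show it as its own descriptive row. Apply the same definition where infants take the mother's serostatus subgroup.

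This is a one-line change. The four-category variable is already derived for Table 8, so no new data are needed. The cost is that inactivated-vaccine recipients leave this one descriptive contrast; they stay in every other analysis and remain visible in the separate row.
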